### 3 STUDY OBJECTIVES

#### 3.1 Primary objective

The **main objective** of this multicenter, non-interventional study is to evaluate disease activity in moderate to severe inflammatory bowel disease (IBD) patients [active Crohn's disease (CD) defined as the Harvey Bradshaw Index (HBI) score  $\geq 8$  or Crohn's Disease Activity Index (CDAI)  $\geq 220$  points at Day 1; active Ulcerative colitis (UC) defined as 9-point partial Mayo score  $\geq 5$  at Day 1].

#### 3.2 Secondary objectives

The **secondary objectives** of the study include:

- Characterization of socio-demographic and clinical aspects of moderate to severe IBD;
- Characterization of treatment patterns for IBD in the previous 3 years, including the use of biologic therapies and failure to these therapies (if any);
- For each type of IBD: comparison of patients with moderate to severe disease activity with patients with no or mild disease activity, regarding socio-demographic and clinical variables of interest and treatment patterns;
- For patients with active IBD in the study appointment (Day 1):
  - Assess clinical activity after a 12 months of follow-up;
  - Description of physician's drivers for therapeutic decision during the 12-month follow up period;
- Evaluation of the quality of life (SF-36, EQ-5D and IBDQ) in moderate to severe IBD patients;
- Evaluation of the work productivity impairment (WPAI) experienced by moderate to severe IBD patients;
- Description of the use of health resources related with the management of IBD in the previous 3 years;
- Estimation of UC or CD-related health care costs in data from the previous 3 years.

#### 3.3 Study Design

This is a multicenter, non-interventional study designed to evaluate disease control, treatment patterns, burden of disease and health related quality of life among patients with IBD.

This study will have duration of 6 months for the cross-sectional phase, with an additional follow-up of 12 months for the patients included in the prospective phase. During study appointment (Day1) data regarding disease activity, treatment patterns, burden of disease and quality of life will be collected (Figure 1). For patients with active disease at Day 1, a 12-month prospective evaluation will be conducted that will allow to follow the course of the disease.

[figure not shown]

Figure 1 – Study Scheme.

## 4 STUDY POPULATION

Study population will include male or female patients aged 18 or older, diagnosed with CD or UC, who comply with all of the inclusion criteria and do not present any of the exclusion criteria.

### 4.1 Inclusion criteria

To be eligible to the subjects must meet all of the following criteria:

1. Male or female;
2. Subjects aged 18 years or older (at the time of diagnosis of moderate to severe UC or CD);
3. Diagnosis of moderate to severe CD or UC for at least 6 months prior to Day 1 appointment according the clinical or endoscopic criteria (23, 24, 25, 26, 27);
4. Subjects provided the written informed consent;

In addition, for the prospective period, eligible patients should present at least one of the following criteria that will only be applied at Day 1:

- For CD patients:
  - HBI  $\geq$  8 points;
  - CDAI  $\geq$  220 points or

Considering that for CD patients, the disease activity may not be clearly documented only with clinical data, some objective criteria may be considered as entry criteria for the 12-month prospective period:

- Colonoscopy in the previous year suggestive of inadequate control of activity or
- Calprotectin levels in the previous year suggestive of inadequate control of activity (i.e. calprotectin  $>200\mu\text{g/g}$ )

- For UC patients: partial Mayo score  $\geq$  5 points.

Note 1: UC patients with no or mild disease activity at Day 1 will not continue to follow up. CD patient with no or mild disease activity at Day 1 but with colonoscopy or calprotectin levels (i.e., calprotectin  $>200\text{ug/g}$ ) in the previous year suggestive of inadequate control of activity will progress to 12-month follow up. Patients that fulfill the above criteria (active disease) will be followed for 12 months, in order to explore patterns of care.

Note 2: Patients with colostomy and prospective period: Although clinical scales defined above are impacted by colostomy these patients will not be excluded from the protocol to ensure the assessment of different clinical presentations of the IBD. In addition, patients with colostomy must follow the same criteria as above to be eligible to the prospective phase.

Note 3: Patients who are eligible for the prospective period, it means, with active disease at Day 1 but who during the 12 months period presents disease remission and/or no activity disease condition, must continue in the study

#### **4.2 Exclusion Criteria**

Any subject that meets at least one or more of the following criteria is not eligible for the study:

1. Indeterminate colitis or not classified colitis;
2. Current or previous participation in interventional clinical trial (within the last 3 years)
3. Presenting mental incapacity, unwillingness or language barriers precluding adequate understanding or cooperation;
4. Hospitalized patients at Day 1;
5. Current off label treatment with vedolizumab.

#### **4.3 Study Discontinuation Criteria**

It will be considered a premature termination the situation in which the subject discontinues the participation, i.e. they are withdrawn from the study before completing the 12 months of follow up period (365 days  $\pm$  14 days from Day 1), due to any of the reasons listed below:

1. Withdrawal of consent: subjects who for any reason withdraw the free and informed consent;
2. Lost to follow-up (no return of the subject on the expected date of visit - drop-out from the protocol);
3. Death;

4. Study termination;
5. Any situation that places the subject within one of the exclusion criteria.

Note: Patients who are eligible for the prospective period, it means, with active disease at Day 1 but who during the 12 months period presents disease remission and/or no activity disease condition, are allowed to continue the participation in the study.

## **5 ANALYSIS ENDPOINTS**

### **5.1 Primary Endpoints**

The primary endpoints of the study are:

- For CD: Proportion of patients with active disease (HBI  $\geq$  8 or CDAI  $\geq$  220 points – based on the criteria used by the site) at Day 1;
- For UC: Proportion of patients with active disease (9-point partial Mayo score  $\geq$  5 points) at Day 1.

### **5.2 Secondary Endpoints**

The secondary endpoints of the study are:

- Distribution of the age, gender, smoking habits, professional status, family history, educational level, subject income by IBD type;
- Distributions of clinical features (e.g.: type of IBD, steroid behavior, anthropometric information, medical history and comorbidities, clinical characterization of the disease) by IBD type;
- Therapies for IBD (aminosalicylates, steroids, immunomodulators, immunosuppressants, biologic products, antibiotics, probiotics, surgery) within the previous 3 years;
- Proportion of biologic-experienced patients;
- Proportion of patients who have not responded previously to biologic therapies and reason;
- IBD treatment introduced at Day 1;
- Socio-demographic, clinical and treatment-related variables in patients with moderate to severe CD (HBI  $\geq$  8 or CDAI  $\geq$  220 points) versus participants with no or mild activity (HBI  $<$  8 or CDAI  $<$  220 points);
- Socio-demographic, clinical and treatment-related variables in participants with moderate to severe activity of UC (partial Mayo score  $\geq$  5 points) versus participants with no or mild activity (partial Mayo score  $<$  5 points);
- Among patients who had moderately to severely active CD at Day 1: HBI or CDAI score after 12 months;
- Among patients who had moderately to severely active UC at Day 1: Partial Mayo score after 12 months;

- Among patients who had moderately to severely active CD or UC at Day 1: Treatment after 12 months; in case of change of current treatment: reason for change;

### Health economics

- Mean score of EQ-5D by IBD type;
- Mean score of different components of SF-36 by IBD type;
- Mean total score of IBDQ and by domain (bowel symptoms, systemic symptoms, emotional function and social function. The IBDQ is not validated for patients with ostomies and therefore should not be applied for these patients);
- Mean of subjects total percentage of work impairment (WPAI);
- Mean work time missed (WPAI);
- Mean impairment while working (WPAI);
- Mean total activity impairment (WPAI);
- Health resources (previous 3 years): drug therapies, imaging and laboratory testing, surgeries, hospitalizations and consultations.

## **6 DETERMINATION OF SAMPLE SIZE**

However, it is expected to include approximately 400 patients regardless of IBD type. This sample size will allow estimates with 95% confidence interval and a margin of error less than 5%. Based on the above and considering an expected ratio of CD/UC of approximately 50%50%, and that the rate of inadequate control of disease activity varies from 20-30% (regardless of the IBD type), it is expected to analyze 40-60 patients with CD and 30-50 patients with UC during the 12-month follow up.

## **7 STATISTICAL ANALYSIS**

### **7.1 General considerations**

As the study is an observational study, epidemiologic methods will be performed in the data analysis. A descriptive analysis will be obtained for all relevant variables, with absolute and relative frequency for categorical variables and mean, standard variation, median, maximum and minimum (or range) for continuous ones. For each study endpoint, data will be summarized by IBD type (CD or UC). The variable normality assumption will be tested using the Kolmogorov-Smirnov test. Non-parametric tests will be used whenever the assumptions for parametric tests are not accepted. Statistical tests will be performed considering bilateral tests and a significance level of 0.05.

All statistical analyses will be performed using the statistical software SAS® (version 9.4; SAS Institute Inc., Cary, USA).

The statistical analysis of the study include a cross-sectional analysis (at the end of the cross-sectional study) and a longitudinal analysis (at the end of the 12-month follow-up period). No interim analyses are planned.

- Cross-sectional analysis: it is expected to obtain a characterization of the study population, the estimation of primary endpoints and the comparison of the subgroups of patients with no or mild activity of disease and those with moderate to severe activity. Hence, for each IBD type, the patients with disease activity will be compared with patients with no or mild activity regarding socio-demographic, clinical and treatment variables of interest. Further details of this analysis are described in Section 7.5 and 7.6.
- Longitudinal analysis will be calculated the proportion of controlled patients after 12-month follow up assessment, as well if applicable, logistic regression will be used for calculating odd ratios and 95% confidence intervals for the patient control at month 12 determined by independent variables. Further details of this analysis are described in Sections 7.5 and 7.6.

## 7.2 Analysis Sets

In this study, they will be analyzed two populations:

- The cross-sectional population will include all patients who have completed the Day 1 assessment (expected to occur 6 months after start of enrolment).
- The longitudinal population will include all patients included in the prospective period (patients with active IBD in Day 1).

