During study appointment (Day1) data regarding disease activity, treatment patterns, burden of disease and quality of life will be collected (Figure 1). For patients with active disease at Day 1, a 12-month prospective evaluation will be conducted that will allow to follow the course of the disease.

At each site, eligible subjects will be identified consecutively as they attend scheduled clinical appointment (Day 1). Upon written consent, data regarding disease activity, treatment patterns, burden of disease and quality of life will be collected from medical records and PRO tools, including quality of life (SF-36, EQ-5D and IBDQ) and work productivity (WPAI) questionnaires. Retrospective data will refer to the previous three years and will include the previous IBD treatments (drug, dose, treatment duration, drug changes, surgeries), and use of other health resources related with the management of IBD.

UC patients with no or mild disease activity at Day 1 will not continue to 12-month follow up. CD patients with no or mild disease activity at Day 1 but with colonoscopy or calprotectin levels in the previous year suggestive of inadequate control of activity will progress to 12-month follow up.

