6.3.1 Inclusion Criteria

Subjects must meet all of the following inclusion criteria:

- 1) Male or female;
- 2) Subjects aged 18 years or older (at the time of diagnosis of moderate to severe UC or CD);
- 3) Diagnosis of moderate to severe CD or UC for at least 6 months prior to Day 1 appointment according the clinical or endoscopic criteria (23, 24, 25, 26, 27);
- 4) Subjects who provided the written informed consent.

In addition, for the prospective period, eligible patients should present at least one of the following criteria that will only be applied at Day 1:

- For CD patients:
 - HBI \geq 8 or
 - CDAI \geq 220 or

Considering that for CD patients, the disease activity may not be clearly documented only with clinical data, some objective criteria may be considered as entry criteria for the 12-month prospective period:

- colonoscopy in the previous year suggestive of inadequate control of activity
or
- calprotectin levels in the previous year suggestive of inadequate control of activity (i.e. calprotectin >200ug/g) (28).

For UC: partial Mayo Score ≥5

Note 1: UC patients with no or mild disease activity at Day 1 will not continue to follow up. CD patient with no or mild disease activity at Day 1 but with colonoscopy or calprotectin levels (i.e. calprotectin >200ug/g) in the previous year suggestive of inadequate control of activity will progress to 12-month follow up.

Patients that fulfill the above criteria (active disease) will be followed for 12 months, in order to explore patterns of care.

Note 2: Patients with colostomy and prospective period:

Although clinical scales defined above are impacted by colostomy these patients will not be excluded from the protocol to ensure the assessment of different clinical presentations of the IBD. In addition, patients with colostomy must follow the same criteria as above to be eligible to the prospective phase.

Note 3: Patients who are eligible for the prospective period, it means, with active disease at Day 1 but who during the 12 months period presents disease remission and/or no activity disease condition, must continue in the study.

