- Health resources (previous 3 years) will be described by IBD group and by disease activity, for the following events: drug therapies, number and type of imaging and laboratory testing, surgeries, number, reason and duration of hospitalizations, number and type of consultations with gastroenterologists or other medical specialists and adverse events.
- Health Care Resource Costs
Costs will be reported in total and on a per patient per month basis. Costs will be obtained by multiplying resource use with relevant unit costs. Unit costs for resource items will be collected by in Brazilian reliable administrative databases or other sources.

UC or CD-related health care costs. Consumer price index (CPI)-adjusted IBD-related health care costs will be computed as total costs, medical costs, drug costs, and other costs.

Treatment pattern costs. Treatment pattern costs will be calculated as total UC or CD-related health care costs, stratified by the defined treatment patterns.

In addition to the descriptive cost data, multivariate cost models may be developed where the observation time is divided into intervals of equal length.

For patients with active IBD at study appointment (Day 1), and included in the prospective period, the following analysis will be conducted:

- Descriptive statistics will be presented in a summary table, for the main socio-demographics, clinical characteristics and treatment regimen of the included patients at Day 1 (baseline), by IBD disease.
- The proportion of patients with active CD after 12 months among patients who had moderately to severely active CD at Day 1 (baseline) will be expressed as percentage and determined as

$$\frac{CD \text{ patients with } HBI \geq 8 \text{ or } CDAI > 220 \text{ after 12 months}}{Total \text{ CD patients with } HBI \geq 8 \text{ or } CDAI > 220 \text{ at Day 1}} \times 100$$

- Similarly, the proportion of patients with active UC after 12 months among those who had moderately to severely active UC at Day 1 (baseline) will be expressed as percentage and determined as:

$$\frac{UC \text{ patients with partial Mayo score } \geq 5 \text{ after 12 months}}{Total \text{ UC patients with partial Mayo score } \geq 5 \text{ at Day 1}} \times 100$$

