- Patients that had light or no activity of disease at the end of the 12-month follow-up will be compared with patients that remained with active disease, regarding socio-demographic, clinical and treatment variables of interest. Similarly to the cross-sectional analysis, the comparison of categorical variables will be conducted with Chi-square or Fisher exact tests and t-student or Mann-Whitney tests will be used to compare quantitative variables.
- If applicable, variables associated with having light or no activity 12 months after baseline will be identified through logistic regression models for each IBD disease and OR (95%CI) will be presented.

- In addition, survival analysis with Kaplan Meier curves and Cox regression models will be used (if applicable) to identify factors associated with achieving light or no activity with baseline treatment (continued or initiated at baseline), during follow-up. In this analysis, patients that remained with active disease or that change treatment due to lack of disease control will be censored and, conversely, success will be defined as having light or no active disease. Time to success will be considered as dependent variable in survival analysis methods.
- The number and reason for treatment changes during follow-up will be summarized and treatment patterns during prospective period will also be described. Patients with treatment changes will be compared with those without changes, regarding main socio-demographic, clinical and treatment baseline variables. The comparison of categorical variables will be conducted with Chi-square or Fisher exact tests and t-student or Mann-Whitney tests will be used to compare quantitative variables.
- If applicable, Poisson regression models based on generalized linear equations will be used to examine the relationship between variables of interest and the incidence of the treatment changes during follow-up.

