- For each IBD (CD and UC), a descriptive statistical analysis (global and according to disease activity) of health resources (the previous 3 years) will be performed for the following events: drug therapies, number and type of imaging and laboratory testing, surgeries, number, reason and duration of hospitalizations, number and type of consultations with gastroenterologists or other medical specialists and adverse events.
- A description of the health care resource costs will be presented. Costs will be reported in total and on a per patient per month basis. Costs will be obtained by multiplying resource use with relevant unit costs. Unit costs for resource items will be collected by in Brazilian reliable administrative databases or other sources:
  - UC or CD-related health care costs:

- Consumer price index (CPI)-adjusted IBD-related health care costs will be computed as total costs, medical costs, drug costs, and other costs;
- Treatment pattern costs:
  - Treatment pattern costs will be calculated as total UC or CD related health care costs, stratified by the defined treatment patterns.
- Multivariate cost models may be developed where the observation time is divided into intervals of equal length.

The longitudinal analysis will be performed for the longitudinal analysis dataset (patients with active IBD at Day 1 included in the 12 months follow-up period):

- A descriptive statistical analysis will be performed for the main socio-demographic, clinical characteristics and treatment regimen of the included patients at Day 1 (baseline) , by IBD type (CD and UC);
- The proportion of patients with active IBD after 12 months among patients who had moderately to severely active IBD at Day 1 (baseline) will be calculated. The results will be presented as percentage.

- For CD:

CCI

- For UC:

CCI

The 95% confidence interval will be calculated for each estimate

- For each type of IBD (CD or UC), a comparison of patients that remained with active disease with patients that had mild or no activity of disease, after 12 months follow-up, regarding socio-demographic, clinical and related-treatment variables of interest will be performed:
  - For qualitative variables, the assessment of a significant difference between groups will be done using the Chi-Square Test or the Fisher's Exact Test depending if the assumption of cell frequency to be made;

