  - For quantitative variables, the assessment of a significant difference between groups will be made through the t-test for independent samples or Mann-Whitney test in case of non-normality of the quantitative variable distribution;
  - If applicable, for patients with CD and UC, the assessment of independent variables which can be associated with the disease control (no or mild activity) after 12 months

follow-up will be performed using a logistic regression model. The ORs estimates and the respective 95% confidence intervals will be presented.

- If applicable, a survival analysis, with Kaplan Meier curves and Cox regression models to identify factors associated with the time of achieving mild or no activity with baseline treatment (continued or initiated at baseline) (dependent variable) will be performed for each type of IBD. The event of interest will be: have mild activity or no active disease. Thus, patients who remained with active disease or who change treatment due to lack of disease control will be censored and, conversely, success will be defined as having mild or no active disease. The survival analysis will include:
  - A non-parametric estimation of the survival function using the Kaplan-Meier estimator (global and stratified by categories for each categorical variable).
  - A comparison of estimated survival function curves of the different categories in each variable using the Log-Rank non-parametric test.
  - If applicable, the semi-parametric Cox proportional hazards model will be adjusted to identify potential factors associated with the time of achieving mild or no activity with baseline treatment (continued or initiated at baseline). The hazard ratios (HR) estimates and the respective 95% confidence intervals will be presented.
- A descriptive statistical analysis will be performed for the number and reason for treatment changes, as well for treatment patterns during the 12 month follow-up period by IBD type (CD and UC);
- For each type of IBD (CD or UC), a comparison of patients with treatment changes with those without changes 12 month follow-up, regarding main socio-demographic, clinical and treatment-related variables (at baseline) will be performed
  - For qualitative variables, the assessment of a significant difference between groups will be done using the Chi-Square Test or the Fisher's Exact Test depending if the assumption of cell frequency to be made;

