## 8 PROTOCOL CLARIFICATIONS/AMENDMENTS

As the amendments will not affect the data collection plan, this SAP was written in accordance with the information contained in Amendment 1 of study protocol, Version 17 Oct 2016. Since the Amendment was implemented at the end of the recruitment period at only one center and after the recruitment for the remaining centers, the section “Disposition of Subjects” will specify how many subjects were included based on the eligibility criteria described in the Amendment.

The following statistical analysis not described in the protocol should be considered:

- 1) General considerations: for each study endpoint, data will be summarized by study sites. Study sites can be classified as region: PI, BA, MG, GO, SP, PR, RS and RJ (Figure 2). The study sites/region should be considered as independent variable to be included in the regression models for the comparison of patients with no or mild activity with patients with disease activity.

[figure not shown]

Figure 2 – Study sites by region.

- 2) Subject's disposition: The study deposition should also be presented by IBD type and regions.
- 3) Demographic and other characteristics: The descriptive statistical analysis should also be performed by regions.
- 4) Primary Analysis: The proportion of patients with moderate to severe CD or UC should be calculated and compared by regions.
- 5) Secondary Analysis: For cross-sectional analysis dataset the descriptive statistical analysis will be performed also by region. The multivariate logistic regression model should include as independent variables all variables with  $p < 0.020$  in bivariate analysis. Optimized model present only variables with statistical significant OR (Odds Ratio). The region should be included as independent variable. For longitudinal analysis dataset the proportion of patients with moderate to severe CD or UC after 12 month follow-up should be calculated and compared by region. As for cross-sectional analysis dataset, the multivariate logistic

regression model should include as independent variables all variables with  $p < 0.020$  in bivariate analysis. Optimized model present only variables with statistical significant OR (Odds Ratio). The region should be included as independent variable.

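### The SAP describes everyone in the prospective period as active at Day 1, but some Crohn's disease patients enter below the score cut-offs, leaving several secondary 12-month CD analyses with an unclear population

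*SAP*

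**What the plan says.** **Analysis set.** SAP 7.2 states: "The longitudinal population will include all patients included in the prospective period (patients with active IBD in Day 1". SAP 7.6 carries the same description into the longitudinal work, which "will be performed for the longitudinal analysis dataset (patients with active IBD at Day 1 included in the 12 months follow-up period".

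**Meaning of active CD.** The objectives and primary endpoint (Protocol 3 and 10.1.1; SAP 3.1 and 5.1) define active CD by score alone: HBI ≥ 8 or CDAI ≥ 220.

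**Who enters follow-up.** Protocol section 6 also admits "CD patients with no or mild disease activity at Day 1 but with colonoscopy or calprotectin levels in the previous year" that suggest inadequate control. Protocol 1.4 and 6.3.1 and SAP 4.1 repeat this route, with calprotectin above 200 µg/g as the marker. There is no such route for ulcerative colitis (UC), where entry needs a partial Mayo score of at least 5.

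**A second meaning of active.** Note 1 in Protocol 6.3.1, repeated in SAP 4.1, applies the label to anyone meeting any entry criterion: "Patients that fulfill the above criteria (active disease) will be followed for 12 months".

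**Analyses at 12 months.**
- Protocol 10.3 and SAP 7.6 restrict the main active proportion to patients moderately to severely active at Day 1. SAP 8 item 7 does the same for the sensitivity analysis.
- SAP 8 item 5 sets the regional version, which contrasts the regions, differently: "For longitudinal analysis dataset the proportion of patients with moderate to severe CD or UC after 12 month follow-up should be calculated".
- In the Protocol 10.3 comparison, patients who "had light or no activity of disease at the end of the 12-month follow-up will be compared with patients that remained with active disease".
- The survival event in SAP 7.6 is to "have mild activity or no active disease".

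**The concern.** A CD patient who enters on colonoscopy or calprotectin with a score below the cut-off is, by the plan's own definition, already controlled at Day 1. If that patient is analysed with those who were score-active, an unchanged score at month 12 counts as control. In the survival analysis, an unchanged score at a later assessment could count as the event.

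Two things are at stake. The CD regional proportion would mix two groups that start from different states, and the mix may differ between regions. The comparison and the models, which Protocol 6.2 wants in order to find factors associated with achieving control, would partly pick up the route by which a patient entered.

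**Working it through.** **1. Which analyses have a stated denominator?**

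| Analysis | Restricted to score-active at Day 1? |
|---|---|
| Main 12-month active proportion (Protocol 10.3; SAP 7.6) | Yes, in words; the protocol formula is visible |
| Sensitivity analysis (SAP 8 item 7) | Yes, in words |
| Regional 12-month proportion (SAP 8 item 5) | No; assigned to the longitudinal dataset |
| Controlled-versus-active comparison, logistic, Kaplan-Meier/Cox (Protocol 10.3; SAP 7.6) | Unclear |
| Tables 90-96 and 98 | Titled for the longitudinal population |

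Table 90 gives the 12-month prevalence, so the result that is restricted in the text is tabulated under the broader label.

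**2. What does the text say about the unclear ones?** Leaning towards score-active patients:
- the heading in Protocol 10.3, which sets two conditions: "For patients with active IBD at study appointment (Day 1), and included in the prospective period, the following analysis will be conducted";
- the word *remained* for the comparison group;
- the word *achieving* for the survival outcome.

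Leaning the other way are the definition in SAP 7.2, Note 1, SAP 8 item 5 and the table titles. Table 101 refers to patients with moderate to severe disease. That does not decide the matter, since inclusion criterion 3 requires such a diagnosis of everyone enrolled.

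**3. The planned CD number.** From SAP 6: 400 × 0.5 × 0.20 = 40 and 400 × 0.5 × 0.30 = 60. This reproduces the stated 40-60 but does not show whether the extra entrants are counted. The 20-30% is a rate of inadequate control, and the colonoscopy/calprotectin route is described in the same terms.

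**4. Illustration for a pooled CD proportion only.** Let f be the extra entrants' share of the CD set, p the proportion controlled at month 12 among score-active patients, and s the proportion of extra entrants below the cut-off at month 12. The shift in the controlled proportion is

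f × s + (1 − f) × p − p = f × (s − p).

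All three inputs are assumed; the documents give none of them.
- f = 5%, p = 60%, s = 70%: 0.05 × 0.10 = 0.5 points
- f = 10%, p = 50%, s = 85%: 0.10 × 0.35 = 3.5 points
- f = 20%, p = 50%, s = 85%: 0.20 × 0.35 = 7.0 points

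The shift is zero if s = p and changes sign if s < p. For the regional comparison, take two regions that both have p = 50% and s = 85%, one with f = 5% and the other with f = 20%. They would show 51.75% and 57.0% controlled, a gap of 5.25 points produced by entry route alone. The formula does not measure bias in an odds ratio or hazard ratio.

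**The case against.** The strongest reply is that the result that matters most is already protected. That stands: a reader might infer from SAP 7.2 that the main 12-month proportion is diluted, but its denominator is explicit in Protocol 10.3, SAP 7.6 and SAP 8 item 7. What remains is secondary, and the logistic and survival models are planned only if applicable.

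It can also be said that *remained*, *achieving* and the two-condition heading show the intent. They do lean that way. But *remained* describes only the still-active group, and Note 1 gives active disease a second meaning, so the description in SAP 7.2 does not settle who is in. For the regional proportion there is no such wording to rely on.

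Unseen material may resolve this. The SAP 7.6 formulas are blacked out, and the table shells and derived-variables appendix are not available. A flag may exist there.

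Two stronger readings go too far. One might suppose that the Kaplan-Meier curve would start below 1 because these patients have the event at Day 1; Protocol 10.3 places the event during follow-up, and nothing counts Day 1 as an event time. One might also infer that the planned 40-60 leaves no room for the extra entrants; the wording of the 20-30% rate does not support that.

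**Conclusion.** The inconsistency is real, is in current text, and concerns CD only. The regional 12-month CD proportion, as written, includes patients already below the cut-offs at Day 1. The CD comparison, logistic regression and Kaplan-Meier/Cox analyses are ambiguous rather than wrong. If SAP 7.2 is followed literally, unchanged patients can count as controlled and entry route can appear as a predictor of control.

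The size is unknown, because the number of such entrants is not given. The 0.5 to 7.0 points rest wholly on assumed inputs, apply to a pooled proportion, and are positive only when the extra entrants stay below the cut-off more often than score-active patients become controlled. UC, the Day 1 primary endpoint and the main 12-month proportion are not affected by this point. It should be fixed before the longitudinal analysis, as a matter of definition.

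A separate, minor mismatch concerns the activity rule. The endpoint is CDAI ≥ 220 (Protocol 10.1.1; SAP 5.1), while the formulas in Protocol 10.2 and 10.3 and SAP 7.5 use > 220. This touches the primary endpoint, but only at a score of exactly 220.

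**What to change.** - In SAP 7.2, keep the longitudinal population for describing treatment patterns. Add a CD subset, score-active at Day 1: HBI ≥ 8 or CDAI ≥ 220 on the instrument the site used.
- Name that subset for the CD results in the regional 12-month proportion (SAP 8 item 5), the controlled-versus-active comparison, the logistic and Kaplan-Meier/Cox analyses, and the matching Tables 90-96, 98, 99, 101 and 103. The UC-only tables (97, 100, 102, 104) need no change.
- Report CD patients who entered only on colonoscopy or calprotectin separately: their number, treatment, and the proportion score-active at month 12.
- Separately, write CDAI ≥ 220 in the formulas so that they match the stated endpoint.

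The cost is SAP wording, table titles and one flag from Day 1 scores already collected. The downside is a somewhat smaller CD set for these secondary analyses. If the planned 40-60 are all score-active, the 95% half-width at 50%, 1.96 × √(0.25/n), is 15.5 to 12.7 points. If extra entrants were 20% of them (assumed), 40 × 0.8 = 32 to 60 × 0.8 = 48 would remain, giving 17.3 to 14.1 points.
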